4.1 Objectives

a) Primary Objective:

1. **Appropriate shocks** as measured by shocks delivered for adjudicated sustained ventricular tachycardia (VT) or ventricular fibrillation (VF) episodes.
2. **Inappropriate shocks** as measured by shocks delivered for all episodes that are not adjudicated sustained VT or VF episodes.

The frequency and rate of appropriate and inappropriate shocks will be measured. The risk of receiving an inappropriate shock will be analyzed. The risk of not receiving appropriate shocks when necessary will also be analyzed.

b) Secondary Objectives

1. **Overall survival** as measured by the ratio of the number of patients that are alive at the end of the use of the WCD to the total population of patients prescribed the LifVest.
2. **Quality of life relative to health state** as measured through the administration of a patient quality of life survey. This survey has been used previously in a published study of patient quality of life.

5. Design of the investigation

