5.1.3 Main Definitions and criteria for evaluating efficacy and safety

Efficacy will be evaluated using the success rate of appropriate shocks. In order for a shock to be appropriate, it must be administered while a patient is experiencing either sustained VT or VF. Otherwise, the shock is inappropriate.

The risk associated with the use of LifeVest will be assessed in terms of inappropriate shocks. Any shock administered to a patient who is not experiencing either VF or sustained VT at the time of administration is an Inappropriate Shock. Even if the patient experiences VT or VF and the condition resolves by itself or bystanders intervention just prior to administration of the shock, it would be classified as Inappropriate.

The classification of individual shocks into the categories of Appropriate and Inappropriate is quite unambiguous, so long as the ECG signal is of sufficient strength to be able to accurately determine the heart rhythm. If the signal is obscured by noise and it is not possible to unambiguously determine the rhythm the shock is generally categorized as Inappropriate, because the noise is generally the cause of the false detection.

All appropriate and inappropriate WCD shock deliveries, as well as VT/VF events will be recorded and analyzed by means of precise ECG recording, provided the VT/VF exceeds the programmed rate threshold for event detection by the WCD. ECG recordings are retrievable from a central server to which all WCD data and ECGs will be transmitted automatically. Similarly, all shock-withhold VT/VF events or VT/VF events that terminated spontaneously will be recorded and counted. All potential bradyarrhythmic or asystole events will be recorded. The device is programmed to record events which are slower than 20 beats per minute or have a QRS amplitude less than 200 microvolts (peak to peak), provided the patient does not respond to alarms.

There will be assessment of all ventricular tachyarrhythmic events, either treated by WCD-shock or with shock withheld by the patient. Furthermore, the assessment of the overall outcome (death) and of clinical events (cardiac and non-cardiac), such as hospitalization, heart failure status, ischemic events, ICD implantation, Pacemaker implantation, surgical interventions (CABG or valve replacement) during the period of WCD wearing.

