9.2 Follow-up data (wearing period) of ITT population

The following follow-up data will be described:

- Serious adverse events since inclusion by number of events in groups of
 - Type of event
 - Cardiac arrhythmic
 - Cardiac non-arrhythmic
 - Vascular non-cardiac (including stroke)
 - Cardiovascular without clearly defined other cause
 - Non-cardiovascular
 - Related hospital stay/prolongation of existing hospital stay
 - Causal relationship to WCD
 - Intensity
 - Outcome
 - Criteria for seriousness
- Time to first hospitalization
- Death
 - Cardiovascular
 - Cardiac
 - Vascular non-cardiac (including stroke)
 - Cardiovascular without clearly defined other cause
 - Non-cardiovascular
 - Death during prescription duration
 - Death while wearing the WCD
 - Death related to arrhythmic event
 - Death related to WCD dysfunction
- WCD events

WCD events/patients with WCD events with following event parameters:

- Type of event
- Termination of event
- Response button pressed
- Shock delivered
- Shock appropriate/inappropriate
- Occurrence of technical and non-technical problems during the wearing period
- Return of WCD device (end of therapy) due to:
 - Death
 - ICD implantation
 - Heart transplantation

- LV function improvement
- Patient's wish
- Other reason
- Clinical status on WCD return: Most recent LV-EF value, NYHA classification, risk assessment and if patient is still listed for heart transplantation
- Planned therapy after wearing period:
 - ICD implantation
 - PCI (Angioplasty, Stent)
 - Bypass surgery
 - Implantation of cardiac pacemaker
 - Heart transplantation
 - Implantation LVAD (left ventricular assist device)
 - Therapy with anti-arrhythmic agents
 - Other planned cardiac therapy
- Medication on WCD return

10. Primary analysis on ITT population

1. **Appropriate shocks** as measured by shocks delivered for adjudicated sustained ventricular tachycardia (VT) or ventricular fibrillation (VF) episodes.

- Quantitative analysis of appropriate shocks
- Analysis of the risk of not receiving appropriate shocks when necessary, calculated as number of non-terminated VT/VF events without shock delivery and without response button pressed/ number of VT/VF events

2. **Inappropriate shocks** as measured by shocks delivered for all episodes that are not adjudicated as sustained VT or VF episodes.

- Quantitative analysis of inappropriate shocks

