- The risk of receiving an inappropriate shock, calculated as number of inappropriate shocks/ non VT/VF events

11. Secondary analysis on ITT population

Overall survival as measured by the ratio of the number of patients that are alive at the end of the use of the WCD compared to the total ITT population.

Survival analysis using Kaplan-Meier curves and cox proportional hazard models will be performed to identify impacts on survival and the occurrence of WCD events will be displayed in tables in the following subgroups :

- indication for the WCD,
- medical history, and
- disease etiology: heart failure according to ESC guidelines
 - no HF (LV-EF $\geq 50\%$)

- intermediate HF (LV-EF $\geq 40 - < 50\%$)
- HF (LV-EF $< 40\%$)

12. Efficacy and safety analysis on ITT population

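### SAP section 10 labels shocks per recorded event as the risk of an inappropriate shock, and its missed-shock ratio has a wider denominator than the risk it is meant to describe

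*Combined protocol and SAP*

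**What the plan says.** The objectives (protocol 4.1, SAP 4.1) name two risks: that of receiving an inappropriate shock, and that of not receiving an appropriate shock when one is necessary. SAP section 10 gives each a formula.

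- Inappropriate shocks: "The risk of receiving an inappropriate shock, calculated as number of inappropriate shocks/ non VT/VF events". The parent item counts "shocks delivered for all episodes that are not adjudicated as sustained VT or VF episodes".
- Missed shocks: "calculated as number of non-terminated VT/VF events without shock delivery and without response button pressed/ number of VT/VF events".

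Related text:

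- The device description in the protocol allows up to five shocks.
- Protocol 5.1.3 defines appropriateness by the rhythm at delivery: "Any shock administered to a patient who is not experiencing either VF or sustained VT at the time of administration is an Inappropriate Shock". It also says that "all shock-withhold VT/VF events or VT/VF events that terminated spontaneously will be recorded and counted". Recording of VT/VF applies "provided the VT/VF exceeds the programmed rate threshold for event detection by the WCD".
- Protocol 5.1.3 and 5.3.1.5 also have asystole, slow-rate events and untreated short runs of VT recorded.
- Protocol section 2 puts inappropriate discharges below 1% per month of wear.
- SAP section 5 gives a precision of 0.8 points at a 1% shock rate and 1.8 points at 5%, for 550 patients.

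**The concern.** **(a) Inappropriate shocks.** The numerator counts shocks and the denominator counts device events. Neither patients nor wearing time appears, so the quotient is not the probability that a patient receives an inappropriate shock. One event can bring several shocks, so the quotient is not confined to 0-100%. The denominator depends on what is logged and what is called a non VT/VF event, which the SAP leaves open. Two studies with the same patient experience could report very different figures. The result also cannot be set against the documents' own scales, which are per month of wear (protocol section 2) and per patient (SAP section 5).

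**(b) Missed shocks.** The numerator is limited to events that did not terminate, were not shocked and were not withheld. The denominator is all VT/VF events, including self-terminated and withheld ones, which can never be misses. As an estimate of the risk when a shock is necessary, the figure is therefore too low whenever such events exist. The term *non-terminated* is not defined either.

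The study has no control group and is mainly descriptive, and it is meant to supply efficacy and safety data for reimbursement renewal. These figures are what readers will take away.

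**Working it through.** **1. The plan's own precision figure.** Two-sided 95% Wald half-width, 1.96 × √(p(1−p)/n), with n = 550 patients:

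- p = 1%: 0.83 points (stated 0.8)
- p = 5%: 1.82 points (stated 1.8)

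Both reproduce with patients as the denominator. With 1,200 patients they become 0.56 and 1.23 points. The documents state no figure for either section 10 formula. This precision does not carry over to a ratio whose denominator is an unknown number of events.

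**2. Inappropriate shocks.** Documented inputs: about 1,200 patients (SAP section 5), mean wear of about 3 months (protocol 5.2.8), range 1 to 6 months (protocol 5.1.1). Assumed: 12 patients with an inappropriate shock, one shock each.

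Patient risk = 12/1,200 = 1.0% (Clopper-Pearson 95% CI 0.52-1.74%), whatever is logged.

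| Recorded non VT/VF events (assumed) | SAP ratio |
|---|---|
| 200 | 12/200 = 6.0% |
| 1,000 | 12/1,000 = 1.2% |
| 10,000 | 12/10,000 = 0.12% |

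Rate per 100 patient-months, with exact Poisson 95% CI:

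| Mean wear | Patient-months | Rate |
|---|---|---|
| 1 month | 1,200 | 1.00 (0.52-1.75) |
| 3 months | 3,600 | 0.33 (0.17-0.58) |
| 6 months | 7,200 | 0.17 (0.09-0.29) |

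Stopping person-time at the first shock hardly matters. At 3 months' wear it removes about 12 × 3 = 36 patient-months at most, giving 12/3,564 = 0.34.

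**3. Missed shocks.** Assumed: 100 VT/VF events, of which 40 self-terminated, 30 were withheld, 28 were shocked and 2 were missed, with no overlap.

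- SAP section 10: 2/100 = 2.0% (exact 95% CI 0.2-7.0%).
- Among events neither self-terminated nor withheld: 2/(2 + 28) = 2/30 = 6.7% (0.8-22.1%).

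If *non-terminated* means not self-terminated, and s is the self-terminated or withheld share, then missed/all = [missed/(missed + shocked)] × (1 − s). With the bracket held at 6.7%:

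| s | SAP figure |
|---|---|
| 10% | 6.0% |
| 50% | 3.3% |
| 70% | 2.0% |
| 90% | 0.7% |

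These event-level intervals treat events as independent. Clustering within patients would probably widen them.

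**4. Recovery from other planned output.** SAP 12.1 reports shocked over all VT/VF events, here 28/100. Combining it with section 10 gives 2.0/(2.0 + 28.0) = 6.7%. This requires the same event set and the reading of *non-terminated* used above. If one of the two misses ended by other means and is classed as terminated, the same step gives 1/29 = 3.4%.

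**The case against.** The case for leaving the plan alone has real force on four points.

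- **Patient-level reporting.** A reader might infer that the patient-level risk of an inappropriate shock will go unreported. The documents do not support that. SAP 9.2 tabulates patients with WCD events by shock appropriateness, and protocol section 6 plans the incidence and frequency of such shocks. What remains is that a different quantity carries the label of risk, with no interval or wear-time rate specified.
- **The missed-shock ratio.** A reader might infer that it is invalid and should be replaced. It is a proper proportion with a coherent meaning: the share of all VT/VF events left unprotected. The conditional alternative is itself a proxy, because nobody knows which shocked events would have stopped unaided. In the example it becomes 2/16 = 12.5% if half the shocked events would have self-terminated, or 1/29 = 3.4% if one of the misses would have. It belongs beside the planned ratio.
- **Conflicting definitions.** A reader might infer that the study has no settled rule for a shock given after the arrhythmia has stopped. Protocol 5.1.3 covers that case, "Even if the patient experiences VT or VF and the condition resolves by itself or bystanders intervention just prior to administration of the shock", and classes the shock as inappropriate. The episode-based wording in protocol 4.1, "shocks delivered for all episodes that are not adjudicated sustained VT or VF episodes", is looser but does not expressly say otherwise. Likewise, non VT/VF may simply be shorthand for not adjudicated as sustained VT or VF. Both need only clarifying words.
- **Values above 100%.** These are algebraically possible, but nothing in the documents suggests they will occur. With the assumed 12 patients at the five-shock maximum (60 shocks), there would have to be fewer than 60 recorded events.

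The unit mismatch in (a) and the unrestricted denominator in (b) survive these points.

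**Conclusion.** The concern holds in two parts of unequal weight, and should be fixed.

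**(a)** The formula is wrong for the quantity it names. At a fixed patient risk of 1.0%, the reported figure ranges from 6.0% to 0.12% across the assumed 200 to 10,000 recorded events.

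**(b)** The formula is valid as a share of all VT/VF events but understates the risk when a shock is necessary, by a factor of (1 − s) under the stated reading of *non-terminated*.

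Confidence is high on the units in (a) and on the direction in (b). The size is not known for either, because the documents give no event counts and no value for s; every count in the two examples is an assumption. No test or decision threshold rests on either ratio, so the damage is confined to how the reported primary results are read.

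**What to change.** **(a) Inappropriate shocks.**

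- Define the risk as patients with at least one inappropriate shock divided by ITT patients, with an exact 95% CI.
- Add first inappropriate shocks per 100 patient-months with a Poisson CI. Count person-time from activation to first inappropriate shock or end of use, based on the wearing period in SAP section 14.
- Keep an event ratio only as a description of the device: shocked events over all recorded events not adjudicated as sustained VT or VF, with the event types listed.
- State that appropriateness follows protocol 5.1.3, and align the episode-based wording in protocol 4.1, SAP 4.1 and SAP section 10 with it.

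**(b) Missed shocks.**

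- Keep the planned ratio, labelled as a share of all VT/VF events, and define *non-terminated*.
- Beside it, report the same misses over adjudicated sustained VT/VF events that neither self-terminated nor were withheld, and show the self-terminated and withheld counts.
- State that this conditional ratio is a proxy and covers only VT/VF above the programmed detection rate.

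**Cost.** The formulas need SAP wording only, since shocks, appropriateness, button use, termination and wearing dates are already collected. Aligning protocol 4.1 needs a short protocol clarification. The conditional missed-shock figure will be less precise and probably less favourable than the planned one, as the intervals in the example show.

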12.1 Primary parameters

- Arrhythmic (VT/VF) events and characterization of event:
 - Number of WCD shocks until termination of the tachycardia event
 - Cardiac arrest immediately after shock delivery
 - Asystole after VT/VF event
 - Maximum heart rate during ventricular tachycardia
 - Polymorphic VT event
 - Immediate ventricular fibrillation (VF)
 - Ventricular tachycardia degenerating into ventricular fibrillation (VF)
- Efficacy will be evaluated using the success rate of appropriate shocks: Number of VT/VF events terminated by shocks/VT/VF events with shock delivery
- Rate of treated VT/VF episodes calculated as shocked VT and VF events/ all VT and VF events
- Cumulative probability of sustained VT/VF, determined according to the Kaplan-Meier method in function of time
- Number of arrhythmic events and shocked events
 - Within 30 days from activation date
 - Within 90 days from activation date

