5.1 General

5.1.1 Description of investigation

France post marketing protocol is an observational study of patients with a prescribed WCD during the time of risk assessment for future potential ICD therapy. Patients who are prescribed a WCD will be asked to participate in the prospective cohort of the study. Patients who have already completed use of LifeVest before start of the study in the corresponding study site can also be asked to consent for use of their clinical data to be included in the retrospective cohort of the study. The retrospective cohort of patients will be analysed separately compared to prospectively included study patients for any variables that are not available for both cohorts, such as the patient survey. Mean WCD wearing time is anticipated to be three months. However, some indications for wearing the WCD may be longer (up to 6 months) or shorter (only one month). For patients who are listed for heart transplantation, the wearing time is scheduled until heart transplantation is performed, or an ICD will be implanted.

5.1.2 Description of the measures to be taken to minimize or avoid bias, including randomization and blinding/masking

There is no randomization of patients enrolled into the study. All consenting patients with a routinely prescribed WCD in the study participating centers will be evaluated, regardless of the length of WCD wearing, including patients who have already completed use of LifeVest before start of the study in the corresponding study site.

The selection bias is limited by the protocol comprehensiveness. There will be no selection, the study will be proposed to all patients receiving LifeVest. In addition, all centres performing implantation of the device will be asked to participate. "Non-participants" will be described.

The attrition bias is also limited (non-existent) as at the end of LifeVest utilization, all material provided to the patient should be returned systematically. Furthermore, the patients follow- up is completely identical to the routine clinical practice. This means that we don't expect to have any difference between the data collected retrospectively and those collected prospectively. However, only patients included prospectively will be asked to complete the quality of life questionnaire.

The prospective cohort of patients will be analysed separately for variables not available for the patients in the retrospective cohort, such as the patient survey.

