5.3.1.4 At LifeVest end of use

- The reason for end of use (death, ICD implantation, heart transplantation, LV function improvement, patient's wish, etc)
- Reports on serious adverse events since the inclusion (ie: cardiac and non-cardiac death, hospitalization, heart surgery/revascularization, arrhythmic events and other cardiac events)

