5.4 Monitoring plan

Authorized, qualified representatives of the sponsor will accomplish on-site monitoring during the study. The accuracy and completeness of core CRF data of a sufficient number of patients will be checked on site against source documents. Details will be given in a risk based monitoring plan.

Quality management will assure that medical data are subject of continuous plausibility checks and data cleaning. The primary outcome parameters consist of follow-up and arrhythmic event raw data which are directly transmitted in clinical routine from the WCD device to a central database to which the treating physician has access via an internet platform enabling him to review any potential arrhythmic event

detected by the device. These data are not modified by human interactions, thus being *per se* valid and do not require source data verification.

6. Statistical considerations and methods

This is a nonrandomized, multicenter observational study. All consecutive LifeVest patients will be asked to participate. Demographic data will be reported on all consenting patients. Thus, all patients in this study will receive LifeVest treatment. Descriptive statistics will be used to report major clinical characteristics of consenting patients, and incidence and frequency of appropriate and inappropriate shocks.

For the overall survival rate calculation, the population of reference will correspond to the total number of patients enrolled who were prescribed the LifeVest.

Standard methods will be used to calculate adjusted survival rates. Kaplan Meier survival curves will be used to report total mortality and wear time. The time to event and census are defined here after.

All reasons for therapy discontinuation will be reported in tabular form.

Event	Decision	Event date or census date
Occurrence of the event	Not censored	Date of the event occurrence
No event and patient followed until the study end	Censored	Date of WCD withdrawal
Lost-to-follow-up	Censored	Date of the last visit or last contact

It is common to use a significance threshold of 5%. This will be applied in this study.

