7.2 Dataset for interim analysis

An interim analysis is planned for reimbursement dossier renewal latest in September 2018. For this purpose a dataset for interim analyses will be generated at a specific point in time defined by the sponsor. The dataset for interim analysis is a data snapshot and will partially consist of uncleaned data because data documentation and cleaning are ongoing at this point in time.

8. General methodology

Continuous variables will be summarized as means (standard deviations [SDs]), quartiles (25 %, 50 % and 75 %), and minimum and maximum value. The number and percentage of patients in each category will be presented for nominal variables. For graphical representation distribution plots, histograms, boxplots and bar charts will be used, as appropriate.

Comparisons of continuous variables will be performed using the Student’s t-test and if assumptions are not met Wilcoxon rank-sum test, and comparisons of nominal variables will be performed using the Pearson’s chi-square test or Fisher’s exact test, as appropriate.

For time-to-event data, the Cox proportional hazards model will be used unless specified otherwise. Survival estimates will be illustrated in Kaplan-Meier plots.

For comparing groups with respect to binary outcomes, logistic regression or analysis of covariance (ANCOVA) will be used as specified.

Statistical comparisons will be performed using two-sided significance tests with alpha=0.05 unless otherwise noted.

9. Demographics and characteristics of ITT population

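### Kaplan-Meier for the cumulative probability of sustained VT/VF censors deaths and transplants and so overstates it: probably slightly in the whole cohort, possibly materially where transplant is frequent

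*Combined protocol and SAP*

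**What the plan says.** SAP 12.1 names the estimator for VT/VF outright: "Cumulative probability of sustained VT/VF, determined according to the Kaplan-Meier method in function of time". SAP 12.2 then repeats the 12.1 parameters in baseline subgroups. WCD indication is one of these, and bridge to transplantation is one of its four categories.

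The general rule in SAP section 8 is "For time-to-event data, the Cox proportional hazards model will be used unless specified otherwise", followed by "Survival estimates will be illustrated in Kaplan-Meier plots". SAP 9.2 lists "Time to first hospitalization" among the follow-up data to be described and names no method for it.

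Protocol section 6 states "Kaplan Meier survival curves will be used to report total mortality and wear time" and adds a short censoring table. The table has three rows: the event occurs; "No event and patient followed until the study end", which is censored at the date of WCD withdrawal; and loss to follow-up, censored at last contact. No row covers a patient who leaves through death or transplantation before the event of interest. The SAP has no censoring table of its own.

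Protocol 5.3.1.4 and SAP 9.2 both record why use of the vest ended, and the listed reasons include death and heart transplantation. For patients listed for transplant, protocol 5.1.1 says that "the wearing time is scheduled until heart transplantation is performed, or an ICD will be implanted". Neither document mentions competing risks or cumulative incidence.

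**The concern.** Kaplan-Meier knows two states, event and censored. A patient who dies or receives a new heart without a prior VT/VF episode is censored at that date. The estimator then assigns to that patient the later VT/VF risk of those still wearing the vest. The patient cannot have that risk, so one minus Kaplan-Meier is larger than the share of patients who have VT/VF during wear. A reader will take a quantity labelled cumulative probability to mean that share.

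The direction of the error is known (upward), and its size grows with the frequency of competing events. If that frequency differs between indications, the curves in SAP 12.2 are raised by different amounts, and part of any difference between them would come from the estimator.

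**Working it through.** **Inputs from the documents.** The expected frequency of shock delivery is 1% to 5% (SAP section 5), used here as a stand-in for the VT/VF probability. The planned sample is 550 and the expected final sample about 1,200 (SAP section 5). Mean wear is three months (protocol 5.1.1).

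**Inputs assumed.** No death or transplant rate is given, overall or by indication. Let q be the probability of death or transplant by the time horizon, on the same one-minus-Kaplan-Meier scale as VT/VF. It is varied from 2% to 50%. Cause-specific hazards are taken as constant.

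**Step 1: the plan's own precision figure, for scale.** The half-width is 1.96 × √[p(1 − p)/n].
- n = 550: 0.83 points at p = 1% and 1.82 at p = 5%. This reproduces the stated 0.8 and 1.8.
- n = 1,200: 0.56 points at 1% and 1.23 at 5%.

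**Step 2: Kaplan-Meier against cumulative incidence.** Let p be one minus Kaplan-Meier for VT/VF, a = −ln(1 − p) and b = −ln(1 − q). The Aalen-Johansen estimator then tends to

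CIF = a/(a + b) × [1 − exp(−(a + b))] = a/(a + b) × [1 − (1 − p)(1 − q)].

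Worked case, p = 5% and q = 40%: a = 0.0513, b = 0.5108, a/(a + b) = 0.0913, and 1 − 0.95 × 0.60 = 0.43. CIF = 0.0913 × 0.43 = 3.92%.

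| Assumed q | CIF when Kaplan-Meier gives 5% | Excess, points | Kaplan-Meier ÷ CIF | CIF when Kaplan-Meier gives 1% |
|---|---|---|---|---|
| 2% | 4.950% | 0.050 | 1.010 | 0.990% |
| 5% | 4.875% | 0.125 | 1.026 | 0.975% |
| 10% | 4.748% | 0.252 | 1.053 | 0.949% |
| 20% | 4.486% | 0.514 | 1.115 | 0.896% |
| 30% | 4.212% | 0.788 | 1.187 | 0.841% |
| 40% | 3.924% | 1.076 | 1.274 | 0.783% |
| 50% | 3.617% | 1.383 | 1.382 | 0.722% |

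At q = 40%, Kaplan-Meier is about 27% above the cumulative incidence (5/3.924 = 1.274). Equivalently, the cumulative incidence is about 22% below Kaplan-Meier (1.076/5).

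**Step 3: scale.** For q of 2% to 10%, the excess at 5% is 0.05 to 0.25 points, well inside the 1.23-point half-width for 1,200 patients. It passes 1.23 points only at q = 50%. A subgroup with so high a rate would have a wider interval of its own, because it holds fewer patients; its size is not stated.

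**Step 4: dependence on what counts as competing.** Suppose every end of use competed, with exponential wear of mean three months. Then b = 1 at three months, so q = 1 − e^(−1) = 63%. A Kaplan-Meier value of 5% becomes 0.0513/1.0513 × [1 − 0.95 × 0.368] = 3.2%, in any indication. How ICD implantation and LV recovery are classed therefore matters as much as the choice of estimator.

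**Step 5: hospitalization.** If Kaplan-Meier were used and gave an assumed 20%, the cumulative incidence with death competing would be 19.8%, 19.5% and 19.0% at q = 2%, 5% and 10%.

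**The case against.** The best defence is that one minus Kaplan-Meier can be a legitimate net quantity: the VT/VF risk for a patient still at risk and still wearing the vest. For comparing arrhythmic tendency between indications, a cumulative incidence has a drawback of its own, since it falls simply because transplant comes sooner. That is fair, and it justifies keeping the Kaplan-Meier curve as a secondary display. It does not rescue the current text, because the SAP states no such estimand and its label points to the probability of the event happening.

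It is also fair that the practical reach is limited. The primary analyses in SAP section 10 are shock counts and event ratios and do not use Kaplan-Meier. SAP 12.1 also gives numbers of events within 30 and 90 days. Deaths, reasons for end of use and time to end of use are all reported, so the competing exits will be visible.

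A reader might infer three stronger points that the documents do not support.
- That Kaplan-Meier is specified for hospitalization. SAP 9.2 names no estimator. Kaplan-Meier follows only from the default in SAP section 8, and the protocol assigns it only to mortality and wear time.
- That transplantation precludes a first hospitalization as death does. It does not; it ends wear and itself involves a hospital stay.
- That the overstatement is greatest in the bridge-to-transplant group. Protocol 5.1.1 makes this plausible, but no rates by indication are given, and listed patients may instead leave through an ICD. Whether other groups are affected as much depends on how ICD implantation and LV recovery are classed.

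**Conclusion.** The point holds for VT/VF in SAP 12.1 and its repeat in 12.2. As written, the plan gives a figure above the probability of actually having VT/VF during wear. At a Kaplan-Meier value of 5%, the excess is 0.05 to 0.25 points if 2% to 10% of patients die or are transplanted first, which is small beside sampling error. It is 0.8 to 1.4 points, or 19% to 38% relative to the cumulative incidence, if 30% to 50% do. The whole-cohort effect is therefore probably small. A material effect in the bridge-to-transplant subgroup is possible because transplant is a planned end of wear there, but it is not demonstrated.

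These sizes rest on constant hazards, on assumed competing rates and on the expected shock frequency standing in for the VT/VF probability. For hospitalization, the finding is only that the method is unspecified. Nothing here undermines the primary shock analyses, and the documents do not tie the reimbursement decision to this curve. This is a worthwhile refinement, not a serious flaw.

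**What to change.** - **SAP 12.1, and its repeat by indication in 12.2:** replace Kaplan-Meier for sustained VT/VF with the Aalen-Johansen cumulative incidence, with death and heart transplantation as competing events. Report 30- and 90-day values with 95% intervals; these match windows already in 12.1.
- **Other reasons for vest return:** state that ICD implantation, LV improvement and the patient's wish are censored at return, or add a sensitivity analysis that treats them as competing.
- **Kaplan-Meier:** it may stay as a secondary curve, labelled as the risk while still at risk and wearing the vest.
- **SAP 9.2:** name the method for time to first hospitalization. If a cumulative probability is reported, use the same estimator with death as the competing event.

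The cost is a few lines in R, the software already planned. Reasons for end of use (SAP 9.2) and its dates (SAP section 14) are already collected, so no new data are needed. The downside is that the reported probability becomes slightly lower.
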